## PURPOSE OF STUDY

The purpose of this clinical study is to determine the effectiveness of the Erchonia Violet ZERONA® Z6 OTC (manufactured by Erchonia Corporation (the Company), an over-the-counter (OTC) laser device, in providing noninvasive body circumference reduction.

## STUDY DURATION

The estimated total duration of the study is 2 weeks.

## INDICATION FOR USE

The indication (claim) being sought through support of the results of this clinical study is:

"The Erchonia Violet ZERONA® Z6 OTC is indicated for use as a non-invasive dermatological aesthetic treatment for the reduction of body circumference."

The Erchonia Violet ZERONA® Z6 OTC is intended for Over-the-Counter (OTC) use.

The indication for use and intended use of the Erchonia Violet ZERONA® Z6 OTC is identical to the predicate device, the Erchonia ZERONA® Z6 OTC, as FDA cleared under K162578:

"The Erchonia ZERONA Z6 OTC is indicated for use as a non-invasive dermatological aesthetic treatment for the reduction of body circumference."

It is cleared for Over-the-Counter (OTC) use.

It is intended that the results of this clinical study be used to support a 510(k) submission to seek FDA clearance to market the Erchonia Violet ZERONA® Z6 OTC for the same indication for use as that cleared for the predicate device, the Erchonia ZERONA® Z6 OTC (K162578), by demonstrating that the efficacy of application of the Erchonia Violet ZERONA® Z6 OTC is non-inferior to the efficacy of application of the Erchonia ZERONA® Z6 OTC (K162578) for the reduction of body circumference of the waist, hips, and bilateral thighs when applied in the over-the-counter setting.

## EXPECTED RESULTS

Following completion of the study treatment administration protocol, it is anticipated that compared with the Erchonia ZERONA® Z6 OTC red diode laser, application of treatment administration with the Erchonia Violet ZERONA® Z6 OTC will yield non-inferior (equivalent or superior) results with respect to mean decrease in subjects' combined waist-hips-bilateral thighs circumference measurements relative to baseline.

# REGULATORY BACKGROUND AND JUSTIFICATION FOR THE CURRENT STUDY

The intended regulatory pathway to seek clearance for the Erchonia Violet ZERONA® Z6 OTC for the intended indication is through a 510(k) submission with supportive clinical data from the outcome of this clinical study protocol.

The intended predicate device is the Erchonia ZERONA® Z6 OTC, previously FDA cleared under K162578.

The Erchonia ZERONA® Z6 OTC is currently FDA cleared under K162578 for use as a non-invasive dermatological aesthetic treatment for the reduction of body circumference. It is cleared for Over-the-Counter (OTC) use.

Preceding its clearance under K162578, the Erchonia Zerona® Z6 OTC received FDA clearance under K143007 for use as a non-invasive dermatological aesthetic treatment for the reduction of circumference of hips, waist, and thighs. K143007 was supported by the results of a Human Factors Validation and Testing Study that evaluated the lay user's ability to operate the device safely, correctly, and effectively per the instructions in the User's Manual. In that study, 22 lay user subjects administered the treatment with the Zerona® Z6 OTC to 22 client subjects. The outcome of that study demonstrated that the lay users successfully understood the information in the User's Manual and were able to follow the instructions to operate the device and administer treatments safely, correctly, and effectively. All treated subjects in that study received an active course of 6 treatments across 2 weeks administered by the lay users. The mean circumference reduction across the waist, hips and bilateral thighs for those subjects was -3.7 inches, a statistically significant finding of equivalency to the precedent prospective randomized controlled trial (RCT) evaluating efficacy of the Erchonia ZERONA® for noninvasive circumference reduction of the waist, hips, and bilateral thighs. In that prior study, 67 males and females aged 18 to 65 years received the identical treatment protocol of 6 treatments with the Zerona® equally spaced across 2 weeks to the waist, hips, and bilateral thighs. The 35 subjects who received the active laser treatment attained an average total circumference reduction of 3.5 inches compared with a mean decrease of 0.68 inches for the 32 subjects who received the sham treatment.

In 2016, the above-mentioned predicate device, the Erchonia® ZERONA® Z6 OTC, received FDA market clearance "for use as a non-invasive dermatological aesthetic treatment for the reduction of body circumference", under 510(k) K162578.

It is intended that the results of the current proposed clinical study be used to support a 510(k) submission to FDA for clearance to market the Erchonia Violet ZERONA® Z6 OTC for the same indication for use as for the Erchonia ZERONA® Z6 OTC as cleared under K162578 by demonstrating that efficacy of application of the two devices are equivalent.

The current clinical study protocol evaluating efficacy of the Erchonia Violet ZERONA® Z6 for the reduction of body circumference is based on the efficacy protocol for the clinical study whose results were submitted in support of clearance of the predicate device, the Erchonia Zerona® Z6 OTC, under K143007.

The 510(k) submitted under K143007 additionally included a successful evaluation of Human Factors Testing and Validation. It is determined that a Human Factors Validation and Testing

study is not applicable for the Erchonia Violet ZERONA® Z6 OTC as the Operational Instructions for Use for the Erchonia Violet ZERONA® Z6 OTC and additional safety and other information contained in the Violet ZERONA® Z6 OTC Installation and Proper Use Reference Guide are identical to those for use of the predicate laser, the Erchonia ZERONA® Z6 OTC, with the only differences being the visible light output (violet compared to red) and the duration of treatment administrations (20 minutes compared to 40 minutes, which is automatically programmed into the device and cannot be altered by the user), neither of which therefore impacts the user's operation of the Violet ZERONA® Z6 OTC versus the ZERONA® Z6 OTC laser device, and therefore has no impact on the user's ability to understand or apply the instructions for use contained in the Violet ZERONA® Z6 OTC Installation and Proper Use Reference Guide or to safely or effectively apply treatments with the device relative to that demonstrated for the predicate device. The study population and all elements of the device protocol and the Violet ZERONA® Z6 OTC Installation and Proper Use Reference Guide other than the pre-programmed administration timing duration (as explained above) will be identical to that employed in evaluation of the Erchonia ZERONA® Z6 OTC device in support of K143007.

Both the predicate and the subject laser devices have the same treatment protocol as will be evaluated for the Violet ZERONA® Z6 OTC in this current study: 6 treatments occurring over 2 weeks: 3 treatments per week; each treatment every other day.

Therefore, as usability has already been established, and all other variables of device user, use, and application are held constant, the goal of this study is solely to demonstrate that efficacy of application of violet light over 20 minutes per treatment administration procedure using the Erchonia ZERONA® Violet Z6 OTC is equivalent to application of red light over 40 minutes per treatment administration procedure using the Erchonia ZERONA® Z6 OTC with respect to reduction in body circumference attained.

The rationale for evaluating efficacy of the application of violet diodes in this current study is that prior research and preliminary testing has demonstrated that non-inferior (equivalent or superior) results with respect to body circumference reduction can be attained with application of violet light compared with application of red light using the same treatment administration protocol but with lesser treatment administration time per treatment administration – 20 minutes versus 40 minutes, respectively, which is a significant time savings to the patient.

## STUDY DEVICE

#### **DEVICE DESCRIPTION**

The Violet ZERONA® Z6 OTC laser is designed for client's seeking noninvasive fat loss without invasive surgery. Violet ZERONA® Z6 OTC allows the patient to continue their daily activities without interruptions from surgery, pain, wounds or garments. The Violet ZERONA® Z6 OTC works by emulsifying adipose tissue which then releases into the interstitial space. The excess fat is then passed through the body during its normal course of detoxification. The Violet ZERONA® Z6 Was built on the clinical foundation of its predecessors, Zerona® and Zerona®-AD, and ZERONA® Z6 OTC, which were proven through clinical studies to be safe and effective in the application of circumference reduction and noninvasive fat loss.

The Erchonia Violet ZERONA® Z6 OTC is identical to the predecessor device, the Erchonia ZERONA® Z6 OTC cleared under K162578, with the differences being light output (visible violet compared to visible red) and duration of treatment administrations (20 minutes compared to 40 minutes, which is automatically programmed into the device). The Installation and Proper Use Reference Guide for use for the Erchonia® Violet ZERONA® Z6 OTC are identical to those for use of the predecessor laser, the Erchonia® ZERONA® Z6 OTC; consisting of the same device set-up and same treatment protocol involving 6 treatments occurring over 2 weeks: 3 treatments per week; each treatment every other day.

The Violet ZERONA® Z6 OTC emits a 405-nanometer wavelength with a tolerance of  $\pm 10$  nanometer, from each of the six specially created and patented electronic diodes. Laser devices are typically constructed to emit a "spot" of light. The Violet ZERONA® Z6 OTC laser utilizes internal mechanics that collects the light emitted from the laser diode and processes it through a proprietary patented lens, and then redirects the beam with a line refractor. The laser applicator heads, each produce an output power of 23mW ( $\pm 2mW$ ) measured. Laser diodes and adjustable laser arms are positioned no greater than 3-4 inches away from the client's target treatment areas.

The Violet ZERONA® Z6 OTC Laser device has been classified by the FDA/EC as a Class II/IIa device and a Class II/2 Laser. This designation represents a current standard for use in order to ensure the safety of the patient. A Class II/IIa Laser is determined to have a chronic viewing hazard. The Violet ZERONA® Z6 OTC Laser device has been classified by the FDA Class II device and a Class 2 laser in accordance IEC 60825-1 (Complies with 21CFR 1040.10 and 21 CFR 1040.11 by Laser Notice #50). The performance parameters and intended use of the Erchonia Violet ZERONA® Z6 OTC are compliant to the internationally recognized safety testing standards for medical devices. The testing of the Violet ZERONA® Z6 OTC device includes functional performance, electrical, safety and component verification, in accordance with the FDA QS requirement, validated annually through ISO 13485 audits. The software incorporated into the operation of the Violet ZERONA® Z6 OTC complies with FDA and ISO Software Development and Validation regulations.

The Violet ZERONA® Z6 OTC laser package is comprised of (1) Violet ZERONA® Z6 OTC Laser device, (1) Pair of Safety Glasses, (1) Power Cord, (1) Power Supply, (1) Tape Measure, and (1) Installation and Proper Use Reference Guide.

### **DEVICE SPECIFICATIONS**

- 1. Laser Head Assembly
- 2. Laser Output Head
- 3. Power Pushbutton
- 4. Boom Arm
- 5. Arm Lock
- 6. Touch Screen
- 7. Main Upright of Base
- 8. Power Inlet
- 9. Wheel Locks
- 10. Electrical Connector
- 11. Locking Knob
- 12. Power Cord
- 13. External Power Supply

Fig. 1

#### Device

- Weight: 71lbs / 32kg
- Height: 70 in / 177.8 cm (Average Adjustable)
- Full Color Touch Screen Control Center
- Four independent Adjustable Arms
- 4 locking Anti-static casters
- Powder coated metal frame
- Non-allergenic material finished with black carbon fiber
- Applied Part: Type B
- Leakage Current 0.3 -0.5 µA (Micro Amps)

#### Laser

- Six line generating diode modules
- Output: 23mW + 2mW
- Wavelength: 405 nm +/- 10nm
- Duty Cycle: CW (Continuous 100%)

#### Power

• Source: 100-240VAC 50-60Hz

#### Temperature

- Operating Temp: 59 to 85°F (15 to 29°C) <50% Relative Humidity
- Transporting: -22 to 158°F (-30 to 70°C) <75% Relative Humidity

#### LASER HEAD ASSEMBLY [1]

This six head assembly located on the end of the boom arm accommodates the lens, laser diodes and their associated electronics.

#### LASER OUTPUT HEAD [2]

The aluminum housing located on the end of the flex arms accommodates the lens, laser diodes, motors, and their associated electronics.

#### POWER BUTTON (ON/OFF) [3]

The Power Pushbutton allows the end user to turn the device ON "|" or OFF "O". To turn the device ON the Power Supply (13) must be plugged into the device Power Inlet (8) and the Power Cord (12), with the other end of the power cord plugged into a wall socket. Once connected, the pushbutton will need to be pushed to the ON "|" position to power the device ON. When the pushbutton is in the ON "|" position an LED on the pushbutton will illuminate.

#### LASER ARM [4]

The Laser Arm serves to position the Laser Head Assembly [1] vertically only. It is designed to be adjusted by intentional force from the end user. This allows the end user to lower and raise the Laser Output Heads for proper positioning to the client for accurate treatment distance.

#### ARM LOCK [5]

The Arm Lock is the black lever attached to the side of the Laser Arm. This is a secondary locking mechanism for the laser arm. The arm tension can be adjusted or locked into position with the Arm Lock lever. The lever is pulled out to place it in the desired position then locked back in place before turning.

#### TOUCH SCREEN [6]

The touch screen functions as a display screen and an input panel, providing information to the user and a means to operate the device by touching the appropriate icon.

#### MAIN UPRIGHT OF BASE [7]

The main upright of base supports the laser arm and contains the electrical connector [10] and the Locking Knob [11].

#### POWER INLET/FUSE HOLDER [8]

The device contains an appliance coupler (Power Inlet) and a flexible detachable power cord. This is the location on the device where the power cord is connected. **NOTE:** The power cord must be plugged into the device at this location prior to plugging it into a wall socket. The Power Inlet module also contains a fuse holder. Replacing the fuses is the only service that can be conducted by the end-user.

The device includes a transformer which converts AC input power to match the required DC power output. Only a 3-prong power cord is required (Hospital Grade Only). Once the power cord is affixed to the power inlet, the opposite end is plugged into a wall socket. Input: 100-240V~0.5-1.5A, 50-60 Hz.

#### WHEEL LOCKS [9]

The device includes four antistatic wheels that enable ease for maneuverability. Once the device is transported to the desired location, the wheel locks can be engaged to eliminate excessive movement of the device.

#### ELECTRICAL CONNECTOR [10]

The electrical connector is a two-piece assembly. The electrical connector connects the main head assembly to the base assembly to transfer data and power.

#### LOCKING KNOB [11]

The locking knob is utilized to secure the two-piece assembly [4] & [7], also preventing the laser arm assembly from unwanted rotation during use.

#### POWER CORD [12]

The device contains a hospital grade flexible detachable power cord. The power cord plugs into the external power supply [13] prior to plugging the other end into a wall socket.

#### EXTERNAL POWER SUPPLY [13]

The power supply is an external AC/DC convertor that is required to power the device. The power supply must be plugged into the device power inlet (8) and the power cord (12), with the other end of the power cord plugged into a wall socket, to power the device.

#### **Protective Wear**

The Violet ZERONA® Z6 OTC is classified by the FDA/IEC as a Class 2 laser device. This represents a current standard for use to ensure the safety of the client. A Class 2 laser is determined to have a chronic viewing hazard. Pointing the laser beam directly into the eye and maintaining it there for an extended period could prove to be damaging.

To ensure there is no possible instance of residual effect, we have included a pair of specialty glasses for use by the client during protocol. The Laser safety glasses sufficiently and effectively block the laser light spectrum at OD 2+ @ 635nm, OD 0.75 @ 405nm VLT60.

Height: 40 mm Width: 145 mm Length: 165 mm

#### Labeling

The Violet ZERONA® Z6 OTC used in this clinical study is regulated as an investigational device, and as such, will be labeled as follows:

CAUTION – Investigational Device. Limited by Federal (or United States) law to investigational use

Additionally, the diagrams below show the device labeling and their placement and is an excerpt from the Installation and Proper Use Reference Guide.

The device is manufactured in accordance with the Good Manufacturing Practices set forth by the FDA, ISO Standards (International) and CE (Conformité Européenne or European Conformity) standards and testing results per Article 9. The device is a Class I Shock Protection and a Class II Medical device. Each of these governing agencies requires specific labeling. All required labels are affixed according to the relevant codes. Each label is pictured and described in this section. Additionally, the placement of each label on the device is communicated.

The following diagram shows the location of the power supply label, serial number label, power pushbutton label and one of the (2) identified pinch point labels.

## SAFETY

#### **Protective Wear**

The Violet ZERONA® Z6 OTC is classified by the FDA/IEC as a Class 2 laser device. This represents a current standard for use to ensure the safety of the client. A Class 2 laser is determined to have a chronic viewing hazard. Pointing the laser beam directly into the eye and maintaining it there for an extended period could prove to be damaging.

To ensure there is no possible instance of residual effect, we have included a pair of specialty glasses for use by the client during protocol. The Laser safety glasses sufficiently and effectively block the laser light spectrum at OD 2+ @ 635nm, OD 0.75 @ 405nm VLT60.

Height: 40 mm Width: 145 mm Length: 165 mm

## STUDY DESIGN

This clinical study is an open-label single-arm non-inferiority design to evaluate the efficacy of the Erchonia Violet ZERONA® Z6 OTC in providing noninvasive body circumference reduction. As such, all enrolled subjects will receive the active study treatment, and therefore, neither randomization to procedure group nor blinding of the subjects nor investigative parties is applicable.

#### STUDY BLINDING

As all subjects in this study will receive the active procedure administration with the Erchonia Violet ZERONA® Z6 OTC, it is not possible to blind either subjects or investigators (device users).

However, there are two aspects of this study design that assist in supporting elements of blinding:

- (i) The primary efficacy study outcome assessment of body circumference measurements is objective; and
- (ii) As the outcome data from this current study will be comparatively assessed to that of the active treatment group in the predicate device clinical study (the clinical data for the Zerona® Z6 OTC submitted in support of K143007), it is possible to blind the study statistician as to which data set pertains to which study, as the variables for each will be identical. The data from each study will be de-identified and presented to the study statistician simply as 'Group A' and 'Group B' data. The statistician will not be aware of which group A or B contains the current study data and which contains the comparative data. The study statistician will also not be made aware of sample sizes for either analysis group if there is a difference. In this way, study success analysis by the statistician cannot be biased.

#### **INVESTIGATORS / DEVICE USERS**

The respective investigator/device user sample population, defined as those who will be administering the treatments with the Erchonia Zerona® Violet Z6 OTC, will be representative of the population of users (non-medical professionals) who may potentially purchase and operate the Violet ZERONA® Z6 OTC device following clearance. The respective investigators / device users will be the identical user population as that enrolled in the study evaluating efficacy and usability of the Zerona® Z6 OTC device in the 2014 comparative study (predicate) and for whom OTC market clearance of the device was subsequently attained through K143007.

#### SUBJECTS

The study sample population, defined as those who will be receiving the study treatments with the Erchonia Zerona® Violet Z6 OTC, will be identical to the study sample population as defined and enrolled in the reference study and as intended to be the real-world patient population recipients of the device treatments.

#### Subject Sample

Subjects will be males and females 18 years or older who are potential candidates for receiving the course of treatment using the Violet ZERONA® Z6 OTC device and who subsequently satisfy all criteria on the Client Qualification Checklist as verified by the device user.

### Sample Size

There will be a minimum of 22 qualified subjects enrolled in and completing this study.

#### Rationale for Sample Size

Sample size is determined to be identical to the final sample size treated and evaluated in the 2014 Zerona® Z6 OTC comparative study to enable clinically meaningful statistical comparison of outcomes to be performed.

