#### PRIMARY EFFICACY OUTCOME EVALUATION

To determine primary efficacy outcome success, the mean change across all subjects enrolled in this study in combined waist-hips-bilateral thighs circumference measurements at study endpoint relative to baseline will be calculated and compared to the relative mean change attained for treated subjects in the reference study.

As this study is a non-inferiority design, the research hypothesis is that violet diode therapy with the Erchonia Violet ZERONA® Z6 OTC is either equivalent to, or superior to, red diode therapy with the Erchonia Zerona® Z6 OTC in effecting a clinically meaningful reduction in body circumference.

The selected equivalence margin ( $\delta$ ) is ±5%. Therefore, non-inferiority will be established if the mean change in combined circumference measurement for subjects treated with the violet diode laser in the current study is no more than 5% less than the subject group who received treatment with the red diode laser in the predicate reference trial that supported efficacy of the Zerona® Z6 OTC device (K143007).

In the predicate reference study, the mean change in combined circumference measurements across the same 6-treatment 2-week evaluation period was a decrease of 3.72 inches. Therefore, success for the current study will be determined as having been met if the mean change in combined circumference measurements for the subject group in the current study is  $-3.72\pm5\%$  inches (-3.53 to -3.91 inches). This is defined as the maximally clinically acceptable difference for which the range of efficacy values ( $\pm5\%$ ) are "close enough" to be considered equivalent.

Version 1.0

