#### SUPPORTIVE SECONDARY EVALUATIONS

The following two secondary evaluations will be performed to provide direct support for the primary efficacy evaluation outcome are will therefore be assessed with respect to statistical significance of change and/or against pre-determined non-inferiority success criteria.

- (i) T-test for independent samples will be performed to compare the mean change in combined circumference measurements across study evaluation (at endpoint relative to baseline) for subjects treated with the Violet ZERONA® Z6 OTC in the current study to the relative mean change for subjects treated with the ZERONA® Z6 OTC in the reference study treatment group. i.e., between device treatment groups. A finding of the difference being not statistically significant (p>0.05) will provide statistically significant and clinically meaningful support for the equivalency of the efficacy of the two devices.
- (ii) Responder rate analysis will be conducted wherein individual responder success is defined per the reference study as at least a 3.0-inch reduction (≥-3.0 inches) in combined circumference measurements for the waist, hips, and bilateral thighs from baseline to after study treatment completion. The maximally clinically acceptable difference for which the responder rate for the current study subject group is defined is (±5%), that is, 73% +/- 5% (68% - 78%), as the responder rate attained in the reference study was 73%.

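### The sample size of 22 is justified only by matching the 2014 study; no power or precision calculation supports it, and 22 subjects cannot resolve the plan's own 5% margin

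*Combined protocol and SAP*

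**What the plan says.** The Sample Size section sets the number: "There will be a minimum of 22 qualified subjects enrolled in and completing this study". The Rationale for Sample Size section gives one reason: "Sample size is determined to be identical to the final sample size treated and evaluated in the 2014 Zerona® Z6 OTC comparative study", and the purpose is "to enable clinically meaningful statistical comparison of outcomes to be performed". Neither section gives a power, an SD, a significance level or an expected interval width.

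The match itself is correct. The regulatory background describes the earlier study as one in which "22 lay user subjects administered the treatment with the Zerona® Z6 OTC to 22 client subjects".

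The Primary Efficacy Outcome Evaluation section reports that the reference change "was a decrease of 3.72 inches" and sets a margin of 5%. It says of the resulting range: "This is defined as the maximally clinically acceptable difference". Success is stated in two ways:

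- One-sided: the violet mean "is no more than 5% less than the subject group who received treatment with the red diode laser".
- Two-sided: the observed mean lies between -3.53 and -3.91 inches.

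Both are judged on the observed mean alone, with no confidence interval or test. The Supportive Secondary Evaluations section adds an independent-samples t-test against the 2014 data and a responder analysis at 3.0 inches, noting that "the responder rate attained in the reference study was 73" per cent.

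**The concern.** Equal group sizes give balance. They do not determine how small a difference the comparison can detect or exclude. The plan ties its sample size to a clinically meaningful comparison and elsewhere sets 5% as the largest acceptable difference, but nothing connects the two.

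The results are meant to support a 510(k) submission by demonstrating non-inferiority. If 22 subjects cannot resolve 5%, an observed mean inside the limits does not show that the devices differ by no more than 5%, and one outside them does not show inferiority. The report would then claim a resolution that the study does not have.

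**Working it through.** **Figures that reproduce.** The sample size equals the 22 treated clients of the 2014 study. The limits follow from the margin: 3.72 × 0.95 = 3.534 and 3.72 × 1.05 = 3.906, printed as 3.53 and 3.91. The margin is 0.05 × 3.72 = 0.186 inch. The number 22 cannot be reproduced as the output of a power formula, because none is given.

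**SD (assumption).** No SD is printed. If changes are normal with mean 3.72 and 73% reach 3.0 inches, then SD = (3.72 − 3.0)/z(0.73) = 0.72/0.6128 = 1.175 inches. With 16/22 in place of 73% it is 1.19. I use 1.175 and show 0.75 to 1.5 as an illustrative range.

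**Standard errors.**
- One mean against a fixed value: 1.175/√22 = 0.2505.
- Difference of two means, 22 versus 22: 1.175 × √(2/22) = 0.354.

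**95% half-widths.**

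| Comparison | Half-width | % of 3.72 | SD 0.75 to 1.5 | SD needed to resolve 5% |
|---|---|---|---|---|
| Against fixed -3.72 (primary criterion) | 2.080 × 0.2505 = 0.521 inch | 14.0% | 9% to 18% | at most 0.42 inch |
| 22 versus 22 (supportive t-test) | 2.018 × 0.354 = 0.715 inch | 19.2% | 12% to 25% | at most 0.31 inch |

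**Chance that a truly equal device misses the criterion** (true mean -3.72, reference taken as exact).
- Two-sided band: 2 × Φ(−0.19/0.2505) = 44.8% with the printed limits, 45.8% with unrounded limits. The range is 24% to 56% over SD 0.75 to 1.5 (unrounded limits).
- One-sided wording: Φ(−0.19/0.2505) = 22.4%, or 22.9% unrounded. The range is 12% to 28%.
- Half of the two-sided misses are therefore means showing more reduction than 3.91 inches.

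**Chance that a device truly 5% worse passes** (true mean -3.534).
- Two-sided band: Φ((3.91 − 3.534)/0.2505) − Φ((3.53 − 3.534)/0.2505) = 44%.
- One-sided wording: 1 − Φ((3.53 − 3.534)/0.2505) = 51%.

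**Power to show non-inferiority within 0.186 inch when truly equal, one-sided 2.5%.**
- Fixed reference: Φ(0.186/0.2505 − 1.96) = 11%.
- Two-sample: Φ(0.186/0.354 − 1.96) = 7.6%. Using the noncentral t with 42 degrees of freedom it is 7.4%, so about 7%.

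To gauge the gap only: 80% power at this SD needs about 314 subjects against a fixed reference, or about 627 per group. This is not a proposal.

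**The case against.** The strongest objection is that the rationale promises no power, precision or margin. It explains why 22 was chosen, and the match is accurate. A reader might infer that the plan defines clinically meaningful as 5%. It does not: the 5% is called the maximum clinically acceptable difference, while clinically meaningful describes the circumference reduction itself in the hypotheses. It would also be wrong to say that a printed figure is miscalculated. What remains is that the only stated reason for the sample size is a clinically meaningful comparison, and that comparison cannot resolve the one difference the plan declares clinically acceptable.

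A second objection is that an equal device does not simply fail almost half the time. That figure belongs to the two-sided band. Under the one-sided wording, which fits the stated aim of equivalent or superior results, the miss rate is about 23%. The documents contain both wordings, so neither figure can stand alone. Likewise, the 19% half-width belongs to the t-test, and the primary criterion's figure is 14%.

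Third, the SD is inferred from one responder proportion. The exact 95% interval for 16/22 is 50% to 89%. The same back-calculation then gives SDs from about 0.58 inch with no finite upper limit. The individual percentages are therefore illustrative. The direction is not in doubt, because even 0.58 inch exceeds the 0.42 and 0.31 inch needed.

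Finally, 22 is a minimum, but modest over-enrolment would not close a gap of this size.

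**Conclusion.** The concern holds in this form: the sample size has no power or precision basis, and 22 subjects cannot resolve the 5% margin. Assuming normal changes and an SD near 1.18 inches, the resolution is almost three margins against the fixed reference (0.521/0.186 = 2.8) and almost four for the between-study comparison (0.715/0.186 = 3.8). The shortfall holds over the whole illustrative SD range.

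The success rule makes this consequential. Because it uses the observed mean alone, it would call a device exactly 5% worse non-inferior about 44% to 51% of the time, depending on which wording applies. The exact percentages should be replaced with values from the actual 2014 SD, which the sponsor should be able to compute because it plans to give that data set to the statistician.

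**What to change.** 1. **Rationale for Sample Size.** State that 22 was chosen to match the 2014 study and is not powered for the 5% margin. Give the expected 95% half-width and the probability that an equal device meets the criterion. Compute both from the actual 2014 SD and do not print the illustrative values above.
2. **Primary Efficacy Outcome Evaluation.** Reconcile the one-sided and two-sided wordings. Report the mean change, and its difference from the reference, with 95% confidence intervals. Revise the sentence saying when non-inferiority is established: a mean that meets the criterion is reported as a point estimate within 5% of the reference, and non-inferiority is concluded only if the interval excludes a deficit of more than 5%. Say in advance whether that interval treats the reference mean as fixed or counts its error.
3. **Hypotheses.** Align these with the revised rule.

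The change adds no patients and no measurements. It does cost the sponsor something: the stated capability becomes more modest, and a non-inferiority conclusion becomes unlikely for a merely equal device (about 7% to 11% at the assumed SD). Since the study is meant to demonstrate non-inferiority for the 510(k), the sponsor should weigh this before the data are seen.
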